
8. Project Narrative

Treatment of schizophrenia currently includes antipsychotic medications and cognitive therapies which improve some symptoms, but do not sufficiently restore cognitive functioning or reduce psychosocial disability. We hypothesize that medications that specifically target sensory information processing deficits, rather than psychotic symptoms per se, will significantly enhance the benefits of a sensory-based targeted cognitive training (TCT) intervention in patients with schizophrenia. We will complete a randomized, double-blind clinical trial to: 1) confirm that the drug memantine augments TCT learning; 2) determine whether memantine enhances the clinical benefits from a full 30 session course of TCT vs. TCT plus placebo in antipsychotic-medicated schizophrenia patients, and 3) determine if memantine's enhancement of TCT is most effective in biomarker-defined subgroups of patients.

SPECIFIC AIMS: Memantine Augmentation of Targeted Cognitive Training in Schizophrenia

Cognitive impairment affects the majority of patients with schizophrenia (**SZ**) and directly contributes to their psychosocial disability. Unfortunately, treatment approaches designed to improve cognition in SZ have been limited. Recent findings demonstrate that cognitive functioning in SZ can be improved by interventions that leverage neuroplasticity-based perceptual learning mechanisms. “Targeted Cognitive Training” (**TCT**) is a computerized intervention designed to sharpen the acuity and fidelity of sensory information processing through specific exercises that systematically increase demands on early perceptual and attentive processes. For many participants, TCT leads to “bottom-up” gains in perceptual functioning that lead to improvements in verbal learning and memory after 20-30h. While these benefits of TCT are evident at the group level, nearly half of all patients fail to show cognitive gains, even after extended 40-100h courses of TCT. For patients, their families, clinicians and health systems, the costs and logistical complexities associated with these time- and resource-intensive interventions, even under optimized conditions, can be prohibitive.

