Our clinic-based studies yielded key findings related to biomarkers, Sound Sweeps performance, and predictors of therapeutic sensitivity to a full course of TCT. **First**, baseline levels of EAIP predicted TCT learning during 1h of Sound Sweeps. **Second**, SZ patients exhibited clinical, neurocognitive and functional gains after 30h of TCT, and changes in EAIP during the first hour of Sound Sweeps testing predicted neurocognitive and clinical gains after a full 30h course of TCT. In total, these findings with memantine, EAIP, TCT learning, and clinical outcomes provide a strong empirical and conceptual framework for a mechanistically-based hypothesis to be tested via the proposed randomized, placebo-controlled 30h pilot trial of (memantine+TCT) vs. (placebo+TCT). Via the below Aims, this application provides efficient pilot testing of this PACT strategy in antipsychotic-medicated SZ patients, using Go/No-Go criteria to inform a future, fully-powered “Confirmatory Efficacy trial”:

AIM 1 – Replicate previous findings of memantine target engagement on TCT learning: In two, 1h tests, determine if memantine increases Sound Sweeps TCT learning in SZ patients (n=54) vs. placebo.

AIM 2 – Test clinical, neurocognitive and functional impact of memantine on TCT, and its relationship to target engagement: In a 30-session course of TCT over 10 weeks, determine if memantine augments the magnitude, rate and/or durability of TCT-induced gains, and whether these gains are associated with target engagement.

AIM 3 – Explore biomarkers of memantine-induced gains: Determine whether higher basal levels of EAIP (and related functional and neurophysiological measures) or changes in these measures across the first hour of Sound Sweeps predict greater sensitivity to memantine-enhanced clinical, neurocognitive or functional gains among SZ patients receiving combined memantine+TCT.

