C. Approach: This application uses an **experimental therapeutics approach** in an "efficient pilot test" of the hypothesis that MEM will augment TCT-induced learning, and thereby clinical, neurocognitive and functional gains, in antipsychotic-medicated SZ patients. In so doing, this application will advance a PACT model for TCT in two specific ways: 1) building on strong preliminary findings, this application will confirm target engagement and identify biomarkers that predict the effectiveness of MEM-enhanced TCT learning, and 2) this application will provide the first randomized controlled trial to assess the ability of medication-enhanced TCT learning (target engagement) to produce significant and lasting clinical, neurocognitive and functional gains in biomarker-characterized SZ patients. In this way, **this application responds to RFA-MH-18-705**, "Development of Psychosocial Therapeutic and Preventive Interventions for Mental Disorders", which supports *"efficient pilot testing of novel psychosocial therapeutic and preventive interventions for mental disorders... using an experimental therapeutics approach."* Moreover, in this application, *"results, whether positive or negative, will provide information of high scientific utility and... support 'go/no-go' decisions about further development or testing of the intervention."* The application uses a *"novel intervention strategy"* - the PACT model - in a design that will *"replicate target engagement and relate change in the... target/mechanism to clinical benefit."* Findings from this pilot study will **inform a future, fully-powered Confirmatory Efficacy trial**.

This application will confirm target engagement by demonstrating that MEM (20 mg po) enhances APS learning in a Sound Sweeps session in biomarker-characterized AP-medicated SZ patients; these patients will then be randomized to a 30-session RCT of TCT+MEM (n=27) vs. TCT+PBO (n=27). Findings will determine whether MEM augments the known neurocognitive and clinical benefits of TCT, and whether APS "MEM sensitivity" - based on APS gains in 2 test sessions - predicts the therapeutic impact of MEM over a 30-session TCT regimen. Other predictive biomarkers will be explored, including baseline neurocognitive (MCCB scores), ERP (MMN, P3a) / EEG (ASSR, evoked theta band power) measures, and MEM effects on auditory discrimination and on ERP changes across the first Sound Sweeps sessions.

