Staff assessing outcome measures are blind to treatment arm, and for some measures receive training using videotaped and practice interviews until achieving high (ICC>.80) reliability based on 20 assessments by 2 raters. We achieve high inter-rater reliability (e.g., ICC>0.85 for PANSS total), and check for rater drift each 90d.

Specific Procedures: TCT is completed with a dedicated room and equipment. Staff trained with a UCSD-developed “TCT Clinician Competence Assessment” monitor TCT, clarify instructions and provide encouragement as needed. **In the initial “biomarker testing” session (Test 1),** subjects complete 1-h of Sound Sweeps to generate a “Pre-Training APS score” as described previously (Fig. 3) under identical circumstances and timelines as for the Test 2 session described below. Treatment group assignment (PBO vs. MEM) is then made using stratified random sampling (above) and 5-7 days later patients ingest either PBO (n=27) or 20 mg MEM (n=27) 240 min before completing the Sound Sweeps session (“Test 2”). MEM effects on APS learning are assessed both within-subject (APS (Test 1 - Test 2) for MEM group subjects: a key measure of **MEM sensitivity**) and between subjects (APS Test 2, PBO vs. MEM groups). After Test 2, all subjects are prescribed daily PBO or MEM using a standard titration schedule (MEM 5 mg at hs→ 5 mg bid→ 5 mg am/10 mg hs→ 10 mg bid over 3 weeks). Participants return to the laboratory to complete 1h TCT per our established procedures^{2,34}, which includes 5 modules of auditory/verbal processing exercises. Each module increases in difficulty as performance improves: **1) Sound Sweeps; 2) Syllable Identification:** Patients distinguish between 2 similar phonemes (e.g., “ba” vs. “da”), differing only in their voice onset time; **3) Word Matching:** Subjects match short similar-sounding consonant-vowel-consonant words (e.g., bad, dad); **4) Listen & Do:** Subjects reconstruct a spoken series of instructions and use a computer mouse to click icons on the screen in a specified order. This exercise is designed to stimulate verbal WM processes supported by the lateral PFC as well as premotor and motor processes. **5)**

Table 1. “Go” criteria: #1, plus at least one of #'s 2, 3 & 4 ($d>0.5$)

1. **Target engagement:** APS learning, MEM > PBO, p<0.05
2. **Greater** clinical, neurocognitive **or** functional gains:
 - ↓PANSSt, ↑MCCB-C **or** ↑Fnxn: MEM+TCT > PBO+TCT
3. **Faster** clinical, neurocognitive **or** functional gains:

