Aim 1 – Confirm target engagement: The primary dependent measure of target engagement is MEM-enhanced APS learning. APS learning is defined as the reduction in Sound Sweeps APS threshold (ms) Test 1 to Test 2 assessment. Target engagement was demonstrated in Fig. 3⁷⁶, and will be confirmed if APS learning is increased by MEM (note that MEM and PBO groups are matched by Test 1 PBO performance via stratified randomized assignment). As appropriate, effect sizes and inferential statistics are based on standard regression or LME models with random intercepts. A significant interaction between contrast coded drug (PBO vs. MEM) and Test (Test 1 vs. Test 2) predictors on APS learning is a “Go” criteria and confirms target engagement.

Aim 2 – Test clinical, neurocognitive and functional impact of MEM on TCT, and its relationship to target engagement: We will determine if MEM+TCT produces greater, faster or more durable clinical, neurocognitive or functional gains from baseline, compared to PBO+TCT, over a 30-session course of TCT. A Cohen’s $d > 0.5$ for the main effect of drug (PBO vs. MEM) or drug x session (#10, 20, 30) interaction in an LME model is the primary “Go” criteria. The effect of drug assesses “greater” gains. Reverse Helmert contrasts for session assesses “faster” gains. A separate model comparing differences in outcomes at 12-weeks post-TCT assesses “more durable” gains. Secondary analyses will examine whether change in MEM-enhanced APS learning (“within-subject” target engagement; Aim 1) predicts gains in Aim 2 outcome measures.

Aim 3 – Biomarkers of MEM-induced gains: We will determine if baseline levels of specific neurocognitive or EEG-based measures, or changes in specific measures with initial MEM exposure (Test 2 vs. 1), predict greater sensitivity to MEM-enhanced neurocognitive, clinical or functional gains over 30-h of TCT. Regression analyses will assess whether specific candidate biomarkers predict MEM-enhanced gains in outcome measures.

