11. “Negative results... [will] guide further intervention development”? This R33 has clear ‘Go/No-Go’ criteria. If target engagement is not confirmed, we will conclude that this design setting is unsuitable for detecting robust MEM group effects on APS learning. Based on the data (e.g. evidence of MEM bioactivity), we will develop testable hypotheses (e.g. cohort differences) that might account for differential outcomes in the present application. Even if there are not robust MEM effects on APS learning (target engagement), it is possible that heterogeneity in MEM APS sensitivity might reflect meaningful subgroups of patients (e.g. low vs. high attention/vigilance), and that APS MEM sensitivity might still predict (correlate with) MEM enhancement of TCT therapeutic effects. In other words, a lack of a group difference (placebo vs. MEM) would not preclude the utility of MEM APS sensitivity as a predictive biomarker. Conversely, even if target engagement is confirmed, it is possible that group differences (placebo vs. MEM) in therapeutic gains might not be detected. A “valid” negative outcome (e.g. lack of positive MEM effects on outcome measures despite evidence of target engagement and adequate TCT exposure) will indicate that MEM-enhanced APS learning is not sufficient to enhance TCT effects in a clinically-defined SZ cohort. Analyses will then determine if MEM enhances TCT effects in biomarker-defined SZ subgroups. A failure to detect such subgroups would suggest a dissociation between target engagement in the first Sound Sweeps session and therapeutic benefit after 30-h of TCT.

12. This work is feasible. Our study team includes 2 Board Certified Psychiatrists (NS, YJ) with SZ clinical trial experience, a licensed Clinical Psychologist/Neurophysiologist and PI of a BBRF-funded trial of biomarker predictors of TCT in SZ patients (GL), an expert statistician with a career focus on analytic pathways from biomarkers to clinical function in SZ (MT), a UCSD SZ Research Program with a >30 y history of recruiting and testing thousands of psychosis patients in studies with ERPs and other biomarkers proposed in this R33 (published retest stability with 1-year follow-up¹⁴⁰), as well as double-blind, PBO-controlled trials of putative pro-cognitive agents (including MEM) in SZ patients and HS^{48,49,74,104}. We completed and published extensively on a 30-session clinical trial of TCT in SZ patients and with many of the same biomarkers proposed herein.

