"Go/No-Go" decisions are based on traditional statistical significance (Aim 1) and effect sizes (Aim 2). Formal statistical testing is conducted using linear mixed-effects (LME) models; hypothesis tests are 2-sided ($\alpha=0.05$). Model parameters are estimated via the R lme4 package and Cohen's d is estimated via the EMAtools package. Type I errors are minimized by constraining the number of primary analyses; secondary analyses use false discovery rate corrections.

PANSSt scores will be assessed at specific intervals. Because TCT is associated with improvements in both positive and negative symptoms, our *a priori* hypothesis is that a PACT effect will be evident in both positive and negative symptoms. Hence, PANSSt is used as the primary metric of symptomatic gains. A greater reduction in PANSSt score will be detected using data from baseline through TCT 30h, by a significant main effect of group (arm) or a significant interaction of group x session, with post-hoc contrasts revealing significant group differences at TCT 30h. A faster reduction in PANSSt scores will be detected using these same data by a significant interaction of group x session and a significant group difference at a point prior to TCT 30h. A more durable reduction in PANSSt scores will be detected using data from TCT 30h through 12 weeks post-TCT, by a significant main effect of arm or a significant interaction of group x post-TCT day, with post-hoc contrasts revealing significant group differences 12 weeks post-TCT.

Comparable analytic approaches will be used for neurocognition (MCCBc) and function (WHODAS) as described in "Research Strategy". Data will be described as means with SEM. Tests for normalcy will be applied to all data and non-parametric comparisons will be used if normalcy is not demonstrated. The Analysis Set for these data will be all subjects who have completed 30h of TCT and post-TCT clinical, neurocognitive and function assessments. When appropriate, missing data are handled via multiple imputation or full information maximum likelihood estimation.

Secondary regression analyses assess the predictive value of putative biomarkers on clinical, neurocognitive or functional gains from the addition of MEM to TCT. Future studies with larger samples will assess potentially more informative models, e.g. Path Analysis to study moderating effects of APS MEM sensitivity and biomarkers on both indirect (moderated-mediation) and direct paths between treatment and outcome.

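### Aim 3 asks which markers predict benefit from adding memantine, but the plan names no marker-by-arm term and gives conflicting populations

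*Combined protocol and SAP*

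**What the plan says.** **Model.** Under Data Analysis in the Approach, the Aim 3 paragraph ends: "Regression analyses will assess whether specific candidate biomarkers predict MEM-enhanced gains in outcome measures". Section 4.4, under the Go/No-Go heading, says: "Secondary regression analyses assess the predictive value of putative biomarkers on clinical, neurocognitive or functional gains from the addition of MEM to TCT". Neither place gives covariates, an arm term or a marker-by-arm term. The Aim 2 paragraph adds a related analysis, equally unspecified: "Secondary analyses will examine whether change in MEM-enhanced APS learning" predicts the Aim 2 gains. By contrast, the same pages do name interactions for Aim 1 (drug by Test) and Aim 2 (drug by session).

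**Target.** The Project Narrative asks whether memantine's "enhancement of TCT is most effective in biomarker-defined subgroups of patients". The section 4.4 sentence above speaks of gains from adding memantine. The subsection on PACT predictors in Significance itself separates predictors of response to TCT, or to a drug, from predictors of a drug's ability to augment TCT.

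**Population.** Three are stated:
- Specific Aims, Aim 3: markers that "predict greater sensitivity to memantine-enhanced clinical, neurocognitive or functional gains among SZ patients receiving combined memantine+TCT".
- Section 4.4, Secondary Efficacy Endpoint(s), where Aim 3 is listed: analyses of primary and secondary hypotheses include all subjects.
- Section 4.4, Go/No-Go, in the paragraph just before the secondary regressions: the analysis set is those who completed 30 hours of TCT and the post-TCT assessments.

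**MEM sensitivity.** Specific Procedures defines the Test 1 to Test 2 APS difference "for MEM group subjects: a key measure of" MEM sensitivity. The Approach then asks whether this sensitivity, "based on APS gains in 2 test sessions - predicts the therapeutic impact of MEM over a 30-session TCT regimen".

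**The concern.** In a parallel-group trial each patient shows one gain, on memantine plus TCT or on placebo plus TCT. The part of that gain due to memantine is not observed in anyone; it exists only as a difference between arms. A marker of memantine benefit is therefore one whose relation to gain differs between arms.

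The wording that does steer the analyst points to the memantine arm alone: the Aim 3 statement, the definition of MEM sensitivity, and item 11 of the question-and-answer list, where "APS MEM sensitivity might still predict (correlate with) MEM enhancement of TCT therapeutic effects". In that arm a marker of ordinary TCT response and a marker of memantine benefit look the same. The confusion is realistic. The Significance section reports that baseline ASSR and theta activity, and P3a change over the first hour of Sound Sweeps, predicted gains in the group's TCT study, which compared TCT with usual treatment and had no memantine arm. ASSR, theta and P3a measures are candidates again here.

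Under Outcome and Go Decisions, a meaningful predictor would weigh towards Go and could be built into the confirmatory trial. A TCT marker reported as a memantine marker would lend that support wrongly.

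**Working it through.** **1. What each regression estimates.** Write gain = b0 + b1·arm + b2·marker + b3·(arm × marker) + error, with arm = 1 for memantine.
- Slope on the marker in the placebo arm: b2.
- Slope in the memantine arm: b2 + b3.
- Memantine effect at a given marker value: b1 + b3·marker.

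The Aim 3 question concerns b3. A memantine-arm regression estimates b2 + b3, which is non-zero for a pure TCT marker (b2 not zero, b3 = 0).

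**2. The plan's own figure.** The only power statement is for Aim 1: d = 0.5, 80% power, two-sided 0.05, test-retest correlation 0.8, 27 per arm. The SD of a change score is √(2 × (1 − 0.8)) = 0.632. Then n = 2 × (1.960 + 0.842)² × 0.4 / 0.25 = 25.1, so 26 per arm by the normal formula and 27 with the t correction. The figure reproduces. It says nothing about Aim 3, for which no power is stated.

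**3. How often a pure TCT marker would be flagged.** Inputs: 27 randomised per arm and, conservatively, 18 completing (Power analyses; Subject throughput). The correlation r between marker and gain is assumed equal in both arms. The documents give no r for ASSR or theta, or for any primary outcome, so a range is shown.

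Simple check by Fisher's z for the memantine arm alone: rejection probability ≈ Φ(atanh(r)·√(n − 3) − 1.96). At r = 0.30, atanh(r) = 0.3095.
- n = 18: Φ(1.199 − 1.96) = 22%.
- n = 27: Φ(1.516 − 1.96) = 33%.

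Mixed-model simulation, 5,000 trials per scenario: change at sessions 10, 20 and 30, between-session correlation 0.7 (assumed), marker effect growing to r at session 30, random intercept, baseline outcome and three binary strata as covariates, dropout at random. The test is the session-30 contrast at unadjusted two-sided 0.05.

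| Assumed r, both arms | Memantine arm only (18 / 27 completing) | Marker × arm (18 / 27) |
|---|---|---|
| 0.20 | 11% / 15% | 4.6% / 4.9% |
| 0.30 | 21% / 28% | 4.0% / 4.3% |
| 0.40 | 35% / 46% | 4.2% / 3.7% |

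At r = 0.30, changing the between-session correlation to 0.5 or 0.85 leaves the memantine-only figures at 21% with 18 completing and 28% with 27.

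**4. What the interaction test can detect.** In the same simulation, power for r = 0.40 on memantine against 0 on placebo is 21% / 27%. The mean 95% interval half-width for the slope difference is 0.68 / 0.58 SD of gain per SD of marker.

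For the effect of multiplicity, use Fisher's z with standard error √(2/(n − 3)), which is 0.365 at n = 18 and 0.289 at n = 27. With atanh(0.40) = 0.4236 the standardised differences are 1.160 and 1.467. Assume one true effect among k marker-outcome pairs, where the correction acts roughly like Bonferroni.
- k = 10, critical value 2.807: power 5% / 9%.
- k = 30, critical value 3.144: power 2% / 5%.

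**The case against.** **The plan already points to moderation.** The Neurocognition section calls MCCB attention/vigilance a possible moderator, and item 11 promises to look at memantine's effect in biomarker-defined subgroups, which needs both arms. Aim 1 tests the memantine enhancement of APS learning as an interaction, so the same term in Aim 3 could be read that way. This stands as far as it goes. A reader might infer that the plan specifies a wrong model; it does not, because it leaves the model open. But no section writes the term down, and the Aim 3 statement read literally drops the placebo arm.

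**No population is stated.** A reader might infer this from the two regression sentences. It is not so: three populations are stated, and they disagree.

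**Larger error rates.** A reader might quote a pooled regression without interaction, which would flag a pure TCT marker more often still. No section proposes that model; including all subjects does not mean omitting the interaction. Nor is the reported r = 0.58 a fair central value: it relates P3a change to verbal learning, which is not a primary outcome.

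**Multiplicity.** The plan applies false discovery rate correction to secondary analyses. The rates above ignore it and so overstate what the planned procedure would give. This stands, but the correction controls chance findings. It does not turn a test of b2 + b3 into a test of b3.

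**Low stakes and deferral.** Aim 3 is framed as exploration, is not required for Go, and moderation of treatment paths is left to a later trial. This limits the severity. It does not remove the promise, in this trial, to determine whether markers predict memantine-enhanced gains.

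**Conclusion.** The concern holds as a gap in specification. Aim 3 asks a between-arm question, no marker-by-arm term is named, and the three stated populations need reconciling. If the memantine-arm reading were followed, a marker with no bearing on memantine benefit would be significant in about 11% to 46% of trials, against about 5% for the interaction test.

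Those figures assume r of 0.20 to 0.40 equal in both arms, 18 to 27 of 27 completing, dropout at random and unadjusted 0.05. They are error rates only if the memantine-arm result is then called prediction of memantine benefit. The logical point in step 1 does not depend on them. The change should be made, but it does not threaten the Go criteria themselves.

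**What to change.** 1. **Population.** Reconcile the Specific Aims with the two statements in section 4.4. Use both arms and all available data, under the likelihood approach already planned.
2. **Markers measured before randomisation** (Test 1 levels and change within Test 1). Regress change from baseline on baseline outcome, arm, marker and marker × arm, or add these terms to the planned mixed model. Include the stratification factors, but leave out the high/low Test 1 APS-learning stratum when Test 1 APS learning is itself the marker.
3. **Claims.** List the marker-outcome pairs that form the false discovery rate family. Base any statement that a marker predicts memantine benefit on the marker × arm estimate and its confidence interval, reported as exploratory.
4. **Test 1 to Test 2 changes,** including MEM sensitivity and the secondary Aim 2 analysis. Compute them in both arms and report their association with outcome by arm. State that they are measured after randomisation and, in the memantine arm, on drug. Do not describe an association seen only in the memantine arm as prediction of memantine benefit.

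**Cost.** SAP wording and a few model terms; the placebo-arm data are already planned. The drawback is low power for the interaction, so few markers will be declared and the intervals should be reported whatever the p value.
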